1.1. Background and rationale

Cartilage tissue has a limited capacity for self-repair due to its avascular and aneural nature. Articular cartilage injuries that are not properly treated are associated with pain and disability and are known to double the incidence of degenerative joint disorders in the elderly.

Cartilage repair treatments have the potential not only to relieve pain and improve the quality of life for younger patients, but also to slow down or eliminate the need for joint replacement in the elderly. However, current therapeutic options such as arthroscopic debridement, micro fracture, autologous osteochondral grafting and use of allografts suffer from major drawbacks, such as defect-size limitations, long and complex rehabilitation times, donor-site morbidity and limited availability of graft material. Even the more advanced cell-based therapies, in addition to involving technically challenging operations associated with donor-site morbidity and highly variable outcome, provide no fully satisfactory treatment, especially for elderly patients. Moreover, these therapies, comprising mainly the implantation of cells, lack the complex biological and mechanical signals which can be delivered via a more developed (mature) graft. In this trial we will introduce two innovations: 1) the use of autologous nasal chondrocytes (NC) as a cell source superior to articular chondrocytes (AC), thus exploiting the already proven higher and more reproducible properties of NCs regarding proliferation and differentiation capacity, which are less dependent on the age of the donor as compared to AC and 2) the delivery of a mature graft as opposed to an immature graft.

1.2. Objectives

The goal of this trial is to compare the clinical efficacy of a mature graft (i.e., nasal chondrocyte tissue engineered cartilage, N-TEC) with that of an immature graft (i.e., nasal chondrocyte cell activated matrix, N-CAM) for the treatment of cartilage lesions in the knee.

This proposed phase II trial will evaluate whether implantation of a mature cartilage graft improves the clinical efficacy, leading to an increase of at least 10 points in the main primary outcome (KOOS (mean of subscores)). In addition, the integration of the grafts with the surrounding tissues as well as the quality of the repair tissue will be assessed.

Retrospectively data will be analyzed to possibly identify the most suitable treatment (mature or immature graft) in relation to the onset of symptoms (acute vs chronic cartilage lesions). This will require enrolling a total of 108 patients in a multicenter, prospective study involving 5 clinical centers.

2. Study methods

2.1. Trial design

The study will be designed as an unblinded multicenter, randomized phase II study for the comparison of a therapy with a mature versus a therapy with an immature graft.

- mature graft (N-TEC):
 - 1) Nasal cartilage biopsy, performed by Ear-Nose-Throat (ENT)/Plastic surgeon
 - 2) Expansion of cells (2 weeks), seeding onto the collagen scaffold (Chondro-Gide®), followed by 2 weeks of in vitro culture
 - 3) Implantation of the cartilage graft into the knee joint via arthrotomy/mini-arthrotomy, debridement down to subchondral lamella and stable cartilage rim, fixation by sutures (e.g. Monocryl 5-0), no drainage
- immature graft (N-CAM):
 - 1) Nasal cartilage biopsy, performed by ENT/Plastic surgeon Expansion of cells (2 weeks) and seeding into the collagen scaffold (Chondro-Gide®), followed by 2 days of in vitro culture
 - 2) Implantation of the cell-seeded scaffold into the knee joint via arthrotomy/mini-arthrotomy, debridement down to subchondral lamella and stable cartilage rim, fixation by sutures (e.g. Monocryl 5-0), no drainage

This phase II study will be performed as a prospective, randomized and unblinded study. Patients will be enrolled at 5 clinical centers in Basel (CH), Freiburg (D), Zagreb (HR), Milan (I) and Wuerzburg (D). The multicentre study, enrolling a total of 108 patients, is planned for the duration of 4 years including follow-up times of two years for each patient. The study will start with the signature of the informed consent by the first patient and end with the two-year follow up of the last patient. Patients may be asked to participate in a further follow-up up to 5 years based on questionnaires on a voluntary basis.

2.2. Randomisation

Upon enrolment in the study, patients will be given a patient ID and entered into the database myclinicaldata (Medacta) by the PI or designated persons of the respective center. Patients will be randomized to the N-TEC (mature tissue) or N-CAM (immature tissue) group.

A permuted-block (2, 4 and 6 size) randomization method will be performed. A randomization list will be associated to each center, guaranteeing an equal distribution of the two groups in all the centers (center stratification). The list is generated by Sealed Envelope online software application (<https://www.sealedenvelope.com/>).

After the screening phase, patients will be allocated to the randomization group through the electronic data capture (EDC) system, which automatically links the patient to the group correspondent to the free available slot of the randomization list, previously uploaded to the system.

The generation of the sequence from sealed envelope website and its upload into the EDC system, will be managed by the owner of platform, who is not involved in clinical center activities (patient selection, clinical visits, radiological evaluation). The clinical centers personal does not have access to the randomization sequences.

2.3. Sample size

The primary endpoint is the Knee injury and Osteoarthritis Outcome Score (KOOS) measured 24 months after surgery. The score ranges from 0–100; the higher the score, the better the outcome. The null hypothesis is that there is no difference in the primary endpoint between N-TEC and N-CAM ($H_0 : KOOS_{N-TEC} - KOOS_{N-CAM} = 0$). The alternative hypothesis is that N-TEC and N-CAM differ significantly in terms of the primary endpoint ($H_A : KOOS_{N-TEC} - KOOS_{N-CAM} = \delta \neq 0$). An absolute difference (δ) of 10 score points or more is considered clinically relevant. These hypotheses will

determine whether the primary objective, namely that therapy with a mature graft will improve the clinical efficacy for the patient, is met.

Sample size was estimated to be such that it would be able to show the superiority of N-TEC to N-CAM regarding the primary endpoint. Assumptions for sample size calculation were based on a study, in which an increase in a mean overall KOOS score after 18 months of 18 points to a final value of 74.73 with a standard deviation of 17.01 was reported¹. We have assumed that the effect size after 24 months will be at least as big. Sample size was calculated using a resampling method. Each sample size ($n=1, \dots 160$) was evaluated by sampling $R = 999$ times, $n/2$ KOOS scores from a normal distribution with $\mu = 75$ and $\sigma = 17$ for the N-CAM group, and $n/2$ KOOS scores from a normal distribution with $\mu = 75 + \theta$ and $\sigma = 17$ for the N-TEC group. The size of θ was varied between 5 and 15. Values that exceeded 100 were set to 100. N-CAM and N-TEC were tested for a difference in KOOS score using a two-sided t-test. Superiority of N-TEC to N-CAM was declared when the test showed a significant result. Sample size was set to ensure at least 80 % power ($1 - \beta = 0.8$), at a significance level of $\alpha = 5\%$. For this study, 108 patients should be recruited to ensure 97 evaluable patients at a power of 80%, considering an overall drop-out rate of 10%.

2.4. Framework

All endpoints will be analysed for the superiority of N-TEC compared to N-CAM.

2.5. Stratification

Unless explicitly mentioned, analyses will not be stratified.

2.6. Statistical interim analyses and stopping guidance

No interim analysis planned.

3. Data management

All data will be entered in case report forms (CRFs) at the local site. Data collected during the study will be stored in an electronic database “MyClinicalData” provided by the sponsor, generated and administered by Medacta International SA (Switzerland).

3.1. Data export

The entered data will be exported from the trial database to a statistical software package.

3.2. Data validation

Data submitted to the MyClinicalData is systematically verified for its consistency and if an error occurs no insertion will be made. Further data validation and cleaning will be conducted after completion of data entry but before database lock.

4. Statistical principles

4.1. General

All recorded and derived variables will be presented by treatment group (and visits, if appropriate) using descriptive summary tables. Continuous variables will be summarised by mean and standard deviation, or median and quartiles. Categorical variables will be summarised with absolute and relative frequencies. In all summaries, the treatment groups will be displayed in the following order: N-CAM, N-TEC. For all parameters, baseline is defined as the last available pre-treatment value (i.e. the last non-missing value available before randomisation).

4.2. Confidence intervals and p-values

The statistical testing will be two-sided with a significance level of 5%. All tests will be accompanied by an effect measure (N-TEC vs N-CAM) with a 95% confidence interval (95% CI).

4.3. Adherence and protocol deviations

Major protocol deviations are:

- Violation of inclusion or exclusion criteria
- no outcome assessment at 12 or 24 months postop, respectively.

These protocol deviations will be summarised by treatment group using absolute and relative frequencies.

Cross-overs to the other treatment arm are not possible in the setting of this study. Since the treatment itself (implantation) will be done by the surgeons and is a one-time application there is no risk of non-compliance. Surgical procedures will be harmonized by training and written SOPs. Violation of inclusion or exclusion criteria such as further lesions in the knee might become apparent only at the time of surgery, so after randomization. Patients will not be followed-up in that case. In case of missed follow-up appointments, the surgeons will contact the patients and reschedule the visit. Questionnaires will be filled in by the patient directly at the time of follow-up using an eCRF. Adherence to recommendations regarding sport activities cannot be monitored; performance at physiotherapy will be asked of the patient, but not monitored.

4.4. Analysis populations

The population for analysis will comprise all patients as randomized, hence the full analysis set (FAS). This corresponds to an analysis according to the intention-to-treat (ITT) principle. The per-protocol set (PPS) consists of all patients who received the treatment they had been assigned to and will be used for efficacy analyses. The safety population consists of all patients in the FAS and it will be used for the analysis of safety outcomes.

5. Trial Population

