11.4 Planned Analyses

11.4.1 Datasets to be analysed, analysis populations

The **full analysis set (FAS)** consists of all patients who were randomized, regardless of treatment conclusion or loss of follow-up (Intention To Treat principle – ITT).

The **per protocol set (PPS)** consists of all patients who have at least one follow-up measure. Patients in the PPS will be analyzed according to the treatment received without randomization.

The FAS will be used for the primary analysis and the secondary analyses as described. The PPS will be used for sensitivity analyses of the primary analysis and the secondary analyses as described.

Demographics and relevant baseline variables will be summarized for the FAS. Categorical data will be presented as frequencies and percentages. For continuous variables, the lower and upper quartile, the median, the mean and the standard deviation will be presented.

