11.5 Handling of missing data and drop-outs

Careful trial planning and conduct should minimize the occurrence of missing data as far as possible. We will consider bootstrap multiple imputation procedures for the analyses of the FAS. No imputation of missing values is planned for the PPS. Thus, if there are patients lost to follow-up visits, they will not be included in analyses of endpoints measured at later follow ups.

A drop-out rate of 10% was considered for sample size estimation.

All primary and secondary analyses described above will be repeated with the PPS and included as sensitivity analyses.

Document:	Clinical Study Protocol
Version:	V07
Page number:	65 of 80
Acronym	Nose to Knee II

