6.3. Analysis methods

6.3.1 Primary analysis

The primary analysis will be done on the PPS. Missing data will be handled according to section 6.4. Primary objective is to demonstrate in patients younger than 65 years with articular knee

cartilage injuries the superiority of N-TEC to N-CAM, assessing by KOOS measured 24 months after surgery.

The primary endpoint will be analyzed with a linear mixed effects model, including therapy (N-TEC vs. N-CAM; categorical variable) as single explanatory variable (fixed effect), and including study center as random effect variable to account for the multicenter study design.

As a sensitivity analysis, we will analyze the primary endpoint by adjusting for covariates and testing for interactions. The linear mixed-effects model will include therapy (N-TEC vs. N-CAM; categorical variable), onset of symptoms (stratified categorical: acute: ≤ 1 years; chronic: > 1 years) and the covariate baseline KOOS (continuous variable) as explanatory variables (fixed effects). In addition, the model will include the interaction between therapy and onset of symptoms. A significant interaction would indicate that the outcome of the therapy depends on how long the symptoms have been present. Further, study center will be included as a random effect variable in the model to account for the multicenter study design.

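### The SAP's per-protocol set is every implanted patient, with missing scores imputed; making it primary loses both protocol analyses (all-randomised and unimputed per-protocol), and SAP section 7 reports only the switch of set

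*SAP*

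**What the plan says.** **Definition.** Protocol 11.4.1 says that the PPS "consists of all patients who have at least one follow-up measure", analysed by treatment received. SAP 4.4 says that it "consists of all patients who received the treatment they had been assigned to".

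**Deviations.** SAP 4.3 opens a list with "Major protocol deviations are". The list has two items: breach of an eligibility criterion, and no outcome assessment at 12 or 24 months. They are to be tabulated by arm. Neither SAP 4.4 nor any other section uses them to define a set.

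**Missing data.** Protocol 11.5 states: "No imputation of missing values is planned for the PPS". It would consider multiple imputation for the full analysis set (FAS) only. SAP 6.3.1 states: "The primary analysis will be done on the PPS. Missing data will be handled according to section 6.4". Section 6.4 is multiple imputation by chained equations with 20 data sets.

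**Role of the sets.** In the protocol the FAS (all randomised) is primary, and every primary and secondary analysis is repeated in the PPS as a sensitivity analysis. In the SAP the PPS is primary. The sensitivity analyses in SAP 6.3.1 and 7.3 change the model and name no second population.

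**Disclosure.** SAP 7.1 reports that the PPS was analysed in place of the FAS, because two randomised patients were not treated and had no 24-month KOOS. SAP 7.2 and 7.3 concern other changes.

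**The concern.** A set called per-protocol is usually read as patients without major deviations, with observed outcomes. The SAP's set guarantees neither. An implanted patient with no 24-month KOOS is a major deviator under SAP 4.3, yet stays in the primary analysis with an imputed score.

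The protocol planned two views of the primary endpoint: all randomised patients, and an unimputed analysis of those followed up. Agreement between them would have been some evidence that drop-out and imputation do not drive the result. The SAP leaves one hybrid set, which omits untreated randomised patients as a PPS would and imputes as an FAS analysis would. The check on bias is gone. A reader of section 7 would not learn that the PPS was also redefined and its imputation rule reversed. SAP 7.3 describes the observed KOOS distribution, so section 7 was written with outcome data in view, and a complete list of changes matters more for that reason.

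**Working it through.** **1. Who is in each set.** Cross-over is excluded by SAP 4.3, so receiving the assigned treatment is the same as being implanted.

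| Patient | Protocol PPS, 24-month KOOS | SAP PPS, 24-month KOOS |
|---|---|---|
| Randomised, not implanted (SAP 7.1) | not in a 24-month analysis: no observed score, no imputation | out |
| Excluded at surgery before implantation (protocol 7.4) | not in a 24-month analysis: data collection ends at withdrawal (8.5) | out |
| Implanted, no follow-up measure at all | out | in, imputed |
| Implanted, some follow-up, 24-month KOOS missing | dropped from the 24-month analysis | in, imputed |
| Implanted, eligibility violation, KOOS observed | in | in |
| Implanted, no deviation | in | in |

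The documents therefore differ in rows 3 and 4, which are the implanted patients with a missing 24-month score. Neither PPS removes row 5.

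**2. The plan's own figure.** Inputs are from SAP 2.3 and 4.2: means 75 and 85 (a difference "of 10 score points or more is considered clinically relevant"), SD 17, scores above 100 set to 100, two-sided t-test at 5%. "Sample size was set to ensure at least 80 % power". Repeating that simulation with 50,000 runs gives power of 80.4% at 97 patients and 79.5% at 96. Inflation for drop-out: 97 / 0.90 = 107.8, so 108. The design figure reproduces and is not in dispute.

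**3. Size of the SAP's set.** The SAP does not state how many were randomised. Assuming 108, and taking the two untreated patients of SAP 7.1:

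- 108 − 2 = 106
- 106 / 108 = 98%

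**4. How many could carry imputed scores.** The number of implanted patients without a 24-month KOOS is not given. At the planned 10% drop-out:

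- 0.10 × 108 = 10.8, about 11, if the two untreated patients are not counted among the drop-outs;
- 10.8 − 2 = 8.8, about 9, if they are.

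**5. Would an unimputed per-protocol analysis still be informative?** The number removed from 106 is unknown, so a range is assumed. Power is under the same design assumptions.

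| Treated patients removed | n | Power |
|---|---|---|
| 0% | 106 | about 84% |
| 2% | 104 | 82.9% |
| 5% | 101 | 81.8% |
| 10% | 95 | 79.3% |
| 15% | 90 | 76.9% |

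The 106 row treats all scores as observed, so with imputed scores it is an upper bound.

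**The case against.** **The content is disclosed even if the name is loose.** SAP 4.4 gives its definition in one sentence, deviations are tabulated by arm, a CONSORT diagram and a list of withdrawals with reasons are planned, and SAP 7.1 reports the change of set. This stands in part. A careful reader can reconstruct the set, but would have to compare both documents to find the new definition and the reversed imputation rule.

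**The imputation change follows from the switch.** The protocol attached imputation to its primary set, and so does the SAP. That is a fair reading of intent. It does not restore the unimputed analysis, and section 7 does not say it.

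**The SAP removed no deviation-free analysis.** Correct. A reader might infer that the protocol planned one and the SAP dropped it. The protocol's PPS needs only one follow-up measure and never excluded eligibility violators. What is lost is the comparison of two populations and the analysis without imputation.

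**Not every deviator is kept.** A reader might infer from SAP 4.4 that the set retains all major deviators. It does not: the two untreated patients had no 24-month KOOS, so they are deviators and are outside it, as are patients excluded at surgery before implantation. Only implanted deviators are retained.

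**A stricter PPS selects on events after randomisation.** Correct, and in a superiority trial that makes it supportive only. The all-randomised analysis is the more important one to restore.

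**Conclusion.** The point holds for definition, imputation and disclosure. The SAP's PPS is a treated-patients set that keeps every implanted major deviator, differs from the protocol's PPS for implanted patients with missing 24-month scores, and is imputed where the protocol planned no imputation. With it as the only efficacy population, the protocol's FAS primary analysis and its PPS sensitivity analysis both disappear, and section 7 states only the switch.

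The size rests on assumptions: 106 patients if 108 were randomised, and 9 to 11 imputed 24-month scores among the implanted if drop-out was the planned 10%. The true number could be smaller. A reader might infer that the trial's conclusion is affected. The documents give no count of deviators or missing scores, so no effect on the estimate can be shown.

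The stated reason for leaving the FAS, that ITT was impossible because two outcomes were missing, is weak, because SAP 6.4 already provides imputation for missing primary outcomes.

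**What to change.** 1. Rename the SAP 4.4 set the treated (modified ITT) set.
2. Report the all-randomised (FAS) analysis of the primary endpoint, using the multiple imputation already specified in SAP 6.4.
3. Add a sensitivity analysis in a PPS made up of patients who received the assigned graft, have no eligibility violation, and have an observed KOOS at the time point analysed (24 months for the primary endpoint), without imputation. The time-point rule matters: a patient who missed month 12 but has a valid 24-month KOOS should stay in the primary-endpoint PPS. Label the result supportive.
4. List in SAP section 7 the changed PPS definition and the changed imputation rule. Protocol 11.4.6 requires every departure from the planned analysis to be listed and justified in the final statistical report, so the same entries belong there.

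The cost is SAP wording and a few extra runs of the existing model, with no new data. The PPS run may have slightly less than the design power: 79.3% if 10% of 106 treated patients are removed.

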5.1. Screening data

Screening data is not collected in the eCRF but the number of screened patients will be calculated from screening logs.

5.2. Eligibility

Inclusion and exclusion criteria are defined in the study protocol. Data about reason for non-inclusion is not documented in the eCRF and will not be available.

5.3. Patient flow

A CONSORT patient flow diagram will be drawn following the CONSORT 2010 standards.²

5.4. Withdrawal/follow-up

All withdrawals and losses to follow-up will be listed with time points and reasons (if available).

5.5. Baseline patient characteristics

Evaluations of the baseline characteristics will be based on the PPS. They will be presented in a descriptive summary table by treatment group. Continuous variables will be shown as mean and

standard deviation or median and quartiles, categorical variables as absolute and relative frequencies. No statistical comparisons of patient characteristics at baseline will be performed.

6. Analysis based on the Study Protocol

6.1. Outcome definitions

Primary endpoint:

- KOOS score: The primary endpoint is the overall KOOS subjective score at the 24-month visit. The difference in the KOOS-score will be compared between the two groups to assess efficacy of N-TEC.

Secondary endpoints:

- MOCART and 3D MOCART Scores: Assessment of stability and integration
- dGEMRIC evaluation: Assessment of quality of the repair tissue
- A further questionnaire (EQ-5d) at 12 and 24 month and an additional time point (12 month) for KOOS will allow the more detailed analysis of the clinical development of the patient's recovery and elucidate changes in the perceived quality of life before and after treatment.
- Additional secondary endpoint is the number of treatment failure at 24 months. The difference will be compared between the two groups.

Other outcomes:

- Retrospective analysis of primary and secondary endpoint data with regard to the onset of symptoms to identify a possible selection of treatment of acute (onset < 1 years) or chronic (onset >1 years) lesions.
- Subgroup analysis to compare the outcome with regard to the localization of the defect (patella vs. femoral condyle/trochlea)

Safety:

- Any AE and SAEs will be recorded regarding event descriptions, onset, resolution dates and relationship to the IMP. All SADR or SUSAR will be reported to Basel as leading center and the respective authorities.

